1 INTRODUCTION

1.1 BACKGROUND

Pneumonia is an acute respiratory infection that affects the lungs [1]. In this disease, the alveoli (small sacs within lungs) get filled up with pus and fluid making it difficult to breathe [1]. In children under five, the most common presenting features of pneumonia are cough and /or difficult breathing/ lower chest in-drawing with or without fever [1]. Risk factors leading to pneumonia include lack of immunization, air pollution, overcrowding, parental smoking, under nutrition, non-hygienic practices, and pre-existing illnesses such as HIV and measles [2]. Early pneumonia identification and treatment saves lives as in severe cases, it can lead to death [3]. Initiating use of antibiotics upon onset of disease can hamper progression whereas absence of early intervention can have limited impacts even with intravenous antibiotics [4].

Despite the availability of standard pneumonia management guidelines and multiple global efforts, pneumonia continues to be the leading killer of children under five, accounting to around 17% of the total under five deaths globally [5-8]. It has been estimated that annually there are around 120 million episodes of pneumonia among children with around 14 million progressing to severe episodes. Out of these cases, close to 1.3 million children die with 81% of these deaths occurring in children under 2 years of age [6]. 52% of these deaths occur in the Sub-Saharan region and South Asia with main contributions from India, Nigeria, Congo, Pakistan and Afghanistan [9]. In Pakistan, pneumonia contributes to 16% of under-five mortality in the country having a well-defined yet poorly functional healthcare system [10-12].

Healthcare in Pakistan is provided through two sectors; Public and private. The public sector includes community health workers, referred to as Lady Health Workers (LHWs) working under the National Program for Family planning and Primary Health Care. It also includes the First Level Care Facilities referred to as Basic Health Units (BHUs) and Rural Health Centres(RHCs) and district/tertiary care hospitals. The private sector includes the private clinic and private hospitals. The public sector provides healthcare free of cost or with minimal charges whereas the private sector is expensive as patients spend out-of-pocket for health service in this sector. This accounts to the wide difference of quality of care across both the sectors as the public sector is not funded adequately by the government to provide high quality services, due to only 2% of the GDP assigned to healthcare. Irrespective of the public and private sector, case management of pneumonia in children under five is supposed to be followed uniformly across all sectors as training of the healthcare providers is standard across all cadres of care under various programs in the country. Despite that fact, the mortality and morbidity rate due to pneumonia in children under five remains unchanged in the country.

1.2 1.2. RATIONALE FOR STUDY

WHO and UNICEF have developed multiple action/ intervention plans to curb pneumonia related morbidity and mortality in children under five and based on those plans Pakistan has launched multiple national programs. These programs include the National ARI control program which was launched in 1989 with the main objectives of reducing severity and mortality due to pneumonia and rationalize the use of

antimicrobials and other drugs for treatment of ARI [13]. It was supported by WHO, UNICEF and USAID. While the program was ongoing, in 1990, in a National workshop on policy related research action plan, organized by the Ministry of Health, the Ministry of Planning and Development and the Aga Khan University (AKU), ARI was ranked sixth of fifteen priority areas for national policy-linked research [13]. The National ARI Control program continued but WHO soon realized that this disease centric narrow approach has not been able to achieve its desired objectives. Therefore, it developed a more integrated approach and launched it globally as Integrated Management of Childhood Illnesses (IMCI) launched in Pakistan in 1998[14]. The approach in IMCI focused on improving case management skills of health workers, strengthening the health system, and addressing family and community practices. Concerns were raised that this is yet another attempt to launch a child health intervention vertically. Duplicity was very much evident from the fact that ARI existed as an independent program and was also part of the IMCI package. Between 2004-2010 PAIMAN, a USAID funded project was undertaken which focused on improving the status of maternal and newborn health in 10 districts (19% of the national population), which later expanded to 24 districts across the four provinces and Azad Jammu and Kashmir in Pakistan. ARI was an important component in that project [15]. The national Maternal, Neonatal and Child Health program (MNCH) was then launched in 2010 funded mainly by DFID implemented in 36 districts and ended after 5 years [16]. It was focused on strengthening of management and organization mechanism of healthcare delivery systems. Under all these programs, selected health care professionals, both community and facility based, were trained on WHO standard of ARI case management out of the 18,029 specialist doctors, 100,131 general physicians, 27,677 working nurses, 6,741 Lady Health Visitors and over 95,600 Lady Health Workers. Looking at the unchanged mortality statistics, there is a concern that these trainings might have failed to change the case management practices within the community. It is perhaps due to the fact that the monitoring and evaluation was not a strong point of these programs [15-18].

There is limited data within Pakistan which reflects the status of the quality of current pneumonia case management practices throughout the three tiered health system (primary health facilities, secondary care hospitals, and tertiary care hospitals) as well as the private sector. There are a number of approaches which can be used to assess standard case management including recall based patient surveys, questionnaire surveys of knowledge, prescription/chart analysis and use of standardized patients or disguised patients to assess actual practice[19]. Standardized patients (SP) are simulated patients who do not suffer from any disease per se but pretend to have those symptoms. They present in the designated clinics/hospitals and use a pre learnt script to provide a history of illness. The healthcare providers are unaware of the simulation of the cases. Upon taking the visit, the SP is then interviewed on the entire experience and in certain cases a recorder is used to audio record the visit. A disguised patient is one who although suffers from a particular disease but acts as a disguised observer as well and works the same way as a simulated patient. Considering the use of standardized patients (SPs) or disguised patients provides an actual picture of practice, therefore, it has been used extensively most recently [20]. This process provides an assessment of the practitioners' knowledge of appropriate care and the actual care delivered, i.e., adherence to standard treatment guidelines [21].

Such an approach in Pakistan can identify current pneumonia case management practices across the country because to-date no such study has been conducted in this field. The results of this study can help in informing design of future policies and

interventions that can in turn assist in reducing pneumonia related morbidity and mortality.

2 STUDY OBJECTIVES

2.1 OBJECTIVES

2.1.1 Primary Objective

To assess the standard practices of pneumonia case management at three levels of health care; community level, first level care facility and practitioner level, across Pakistan.

To assess the standard practices of pneumonia case management in the private sector across Pakistan.

2.1.2 Secondary Objectives

To determine the differences in pneumonia case management observed across the provinces of Pakistan in both public and private sector.

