5 PARTICIPANT SELECTION AND ENROLMENT

5.1 IDENTIFYING PARTICIPANTS

Data collectors will be licensed healthcare professionals (doctors or nurses) with at least one 6-12 months of experience working in the field of paediatrics. They will be recruited after interviews with the selection team (Investigators and project manager) upon giving advertisements for posts of data collectors.

For selection of the LHWs to observe them, a randomly selected rural community through our computerized system will be generated from where the caregivers will be selected to act as disguised ones. Additionally, a complete list of functional RHCs and BHUs will be obtained from the corresponding district health office (DHO) which is the administrative authority for these centres. From that list, four BHUs and four RHCs per province will be randomly selected using a lottery method. For sampling of the practitioners, a list of tertiary care facilities will be obtained from the health department of each province and a list of private clinic and private hospitals from their corresponding directories. These lists will be used to randomly select five practitioners each from public and private sector. Once the BHU, RHC, private and public practitioner sites have been selected, disguised caregiver will be recruited and observations made. In case a healthcare provider is not available or if a facility has been closed down, the caregiver will be provided an alternate address.

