8 STATISTICS AND DATA ANALYSIS

8.1 SAMPLE SIZE CALCULATION

Considering this is a qualitative study therefore an approximate estimate of the sample will be provided. Event sampling will be employed whereby a pre-defined checklist of behaviours will be developed to record all occurrences. The sample size is based on point of theoretical saturation although we plan to conduct at least 32 observations from each of the four provinces and the federal capital (LHWS; 6, BHU Medical officer; 4, RHC medical officer; 4, private practitioner; 9, and public practitioner; 9). Thus a minimum of 160 observations will be conducted. Data will be collected over a period of six months.

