8.2 PROPOSED ANALYSES

Behavioural coding will be employed to prepare the data for analysis. This means that a predetermined code will be given to each variable against each category of observations (History, examination, diagnosis and treatment). Each variable will be answered as "Y" meaning yes, the task was accomplished and "N" meaning no, the task was not accomplished (section 6.1). Additionally, the responses will be labelled as correct, partially correct and incorrect for history taking and examination. If on history taking, the healthcare provider asks questions on all variables, then the responses will be labelled as correct and if any one variable is missed then the response is indicated as partially correct and in case less than 50% of the variables are asked about, then the responses will be labelled as incorrect. The same labels will be specified for the examination. In case of diagnosis and treatment, the labels will be specified as correct and incorrect only as there is no partially correct diagnosis and treatment regimens. The overall frequencies and percentages of these responses will be calculated and cross tabulated across the provinces.

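### The secondary objective asks for provincial differences within each sector, but section 8.2 plans only percentages by province, with no sector split, interval or estimated difference, so chance gaps can be mistaken for real ones

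*Combined protocol and SAP*

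**What the plan says.** Section 2.1.2 gives one secondary objective: "To determine the differences in pneumonia case management observed across the provinces of Pakistan in both public and private sector".

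Section 8.2 codes each checklist item yes or no. It then labels history and examination as correct, partially correct or incorrect, and diagnosis and treatment as correct or incorrect. It ends: "The overall frequencies and percentages of these responses will be calculated and cross tabulated across the provinces". I found no other analysis text.

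Section 8.1 plans "at least 32 observations from each of the four provinces and the federal capital", split as "LHWS; 6, BHU Medical officer; 4, RHC medical officer; 4, private practitioner; 9, and public practitioner; 9", and concludes: "Thus a minimum of 160 observations will be conducted". On the basis for this number it says: "The sample size is based on point of theoretical saturation". No precision target, power or expected rate is stated.

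Section 5.1 gives a different practitioner count: "These lists will be used to randomly select five practitioners each from public and private sector".

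**The concern.** The objective has two dimensions, province and sector; the planned table has one. Even along that dimension, bare percentages carry no measure of sampling error, and the private sector has only 9 visits per area.

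Sites are selected at random, and section 1.2 hopes the results will help inform future policies and interventions. Readers will therefore generalise beyond the visits made. Followed as written, the plan gives them no means of separating a provincial difference from the scatter expected with cells of this size.

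**Working it through.** **Inputs.** From 8.1, visits per area are LHW 6, BHU 4, RHC 4, private 9 and public practitioner 9. The true rate p of a correct result is not in the documents; it is an assumption, shown from 5% to 50%. Visits are treated as independent, with one rate in all five areas and across provider types.

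**The plan's own figure.** 6 + 4 + 4 + 9 + 9 = 32 per area, and 32 × 5 = 160. This matches 8.1. By sector, each area has 6 + 4 + 4 + 9 = 23 public visits and 9 private visits.

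**Chance gap among five equal areas.** I drew five binomial percentages with the same p, 400,000 times, and took the largest minus the smallest. Mean gap in points:

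| Visits per area | p = 5% | 10% | 20% | 30% | 50% |
|---|---|---|---|---|---|
| All, n = 32 | 9 | 12 | 16 | 19 | 20 |
| Public, n = 23 | 10 | 14 | 19 | 22 | 24 |
| Private, n = 9 | 14 | 21 | 30 | 35 | 38 |

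Chance of a gap of at least 20 points at p = 10% / 20% / 30% / 50%:
- n = 32: 5% / 24% / 39% / 48%
- n = 23: 16% / 45% / 59% / 67%
- n = 9: 67% / 88% / 93% / 95%

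Chance of a gap of at least 40 points at p = 50%: 1.4% (n = 32), about 3.7% (n = 23) and 46% (n = 9).

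**Precision of one provincial difference.** The 95% half-width is 1.96 × √(2p(1−p)/n). At p = 50%:
- n = 32: 1.96 × √(0.5/32) = 24.5 points
- n = 23: 1.96 × √(0.5/23) = 28.9 points
- n = 9: 1.96 × √(0.5/9) = 46.2 points (the normal approximation is rough here)

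At p = 10% the half-widths are 14.7, 17.3 and 27.7 points.

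**Precision of one percentage.** The 95% Wilson intervals are 34–66% for 16/32, 29–67% for 11/23 and 19–73% for 4/9.

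**If section 5.1 governs.** If its five practitioners per sector are per province (the text does not say so), private n = 5, and the mean chance gap at 10% / 20% / 30% / 50% is about 26 / 39 / 46 / 50 points.

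**Would a simple rule on pairwise intervals be enough?** Five areas give 5 × 4 / 2 = 10 pairs. With all true rates at 50%, at least one of the ten unadjusted 95% Newcombe intervals excludes zero in about 33% (n = 32), 30% (n = 23) and 24% (n = 9) of repeats. That is for a single endpoint in a single cell, so unadjusted pairwise intervals would themselves present noise as a finding.

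**The case against.** The strongest reply is that the study is descriptive. Sections 3.1 and 8.1 call it qualitative, the sample rests on saturation, the objective is secondary and speaks of differences observed, and no hypothesis test or ranking of provinces is planned. That stands against demanding a powered comparison. It does not excuse bare percentages: the endpoints are correct/incorrect classifications from randomly selected sites, and saturation says nothing about the precision of a percentage. Nor does it explain the missing sector split.

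The second reply concerns size, and much of it stands. A reader might infer that chance gaps of 20 to 40 points are to be expected for every endpoint and will be read as real. The documents do not support that. They give no rate, and 50% is the least favourable case. Annex C requires 12 of 12 items for correct history and 6 of 6 for correct examination, so rates near zero are plausible for two of the four endpoints. At p = 5% a gap of at least 20 points among areas of 32 visits occurs in only 0.3% of repeats. How readers will react is a forecast; that they could be misled is as far as the text goes.

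Third, raw records are retained under 11.4, so intervals could be added at reporting. That is true, but the plan does not commit to it.

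**Conclusion.** The point holds. Section 8.2 as written cannot deliver the objective in 2.1.2, because it has no sector dimension and gives neither an interval nor an estimated difference.

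The size depends on an assumed rate. For true rates of 10% to 50%, the mean chance gap between best and worst area is about 12 to 20 points overall, 14 to 24 in the public sector and 21 to 38 in the private sector; at 5% it is about 9, 10 and 14. Gaps of 40 points or more are rare by chance outside the private cell.

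These figures assume independent visits. Section 4.1 allows one caregiver to serve the LHW, BHU and RHC visits of a locality where cases are few, so public-sector and overall intervals computed as if visits were independent are probably too narrow. The documents give no correlation, so this was not quantified. Section 4.1 also provides two data collectors per province, so observer effects cannot readily be separated from provincial ones.

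The primary objectives and the data collection are not affected.

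**What to change.** Amend section 8.2 as follows.

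1. Tabulate each endpoint by province within sector, and by provider type within the public sector, with counts, denominators and 95% Wilson or exact intervals.
2. Report provincial differences within each sector with 95% intervals, preceded by one exact global test per endpoint and sector, stratified by provider type in the public sector.
3. Describe no province as better or worse on pairwise intervals unless that global test is significant and the pairwise comparisons are adjusted for multiplicity. Otherwise state that the comparison is descriptive.
4. Record which visits shared a caregiver, and state that intervals treating them as independent are probably too narrow.

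Reconcile the practitioner counts in 5.1 and 8.1 at the same time, since they set the private-sector denominator.

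No extra visits are needed. The cost is analysis wording and a few hours of programming. The downside is that most provincial contrasts will be reported as inconclusive, and strata of 4 to 9 visits will give imprecise estimates.

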2.2 ENDPOINTS

2.2.1 Primary Endpoint

1. Correct history taking of case of pneumonia
2. Correct examination of case of pneumonia
3. Correct diagnosis of case of pneumonia
4. Correct treatment of case of pneumonia

3 STUDY DESIGN

3.1 Methodology:

This will be a qualitative study which will be conducted through participant observations over a period of 13 months across randomly selected sites in four provinces of Pakistan in addition to the federal capital. The provinces are Baluchistan, Khyber Pakhtunkhwa (KPK), Punjab and Sindh.

After obtaining ethical clearance, an observation tool will be developed based on standard WHO guidelines and input from field experts. This tool will be pretested upon finalization. At the same time an advisory committee will also be formulated composed of expert paediatricians and public health professionals who will provide their input into the implementation protocol and the tool. Once the tool is finalized trainings will be conducted on the tool and then observations will be conducted.

3.2 Observation Sites:

Observations sites will be randomly selected from each of the four provinces and the capital through our specialized sampling software. Upon site selection, observations will be made across the following levels of healthcare: community level, first level care facility (FLCF) and practitioner level both in the public and private sector. The community level observations will include observation of the pneumonia case management by the LHWs. LHWs are the primary care givers at the community level who cover around 60% of Pakistan. Their basic duties include education, counselling and basic management of the common maternal and child ailments. Each LHW covers around 100-120 household and visits each household once a month. The observations will be made either at the health house of the LHW or she will be requested to visit the household of the disguised patient.

The FLCF level will include observations made at the primary health care facilities which are the Basic Health Units (BHUs) and Rural Health Centres (RHCs). A basic health unit is located within a union council which is the smallest administrative unit in the Pakistani administrative system. Each basic health unit covers a catchment area of 25,000 households. Pakistan has around 5,290 BHUs although not all are functional. Services provided at BHU are promotive, preventive, curative and referral .LHWs refer patients usually to BHUs. RHCs provide in-patient service as compared to BHUs. They usually have 10-20 beds and cover a catchment area of 100,000 people. The RHC provides promotive, preventive, curative, diagnostics and referral services apart from the in-patient services. It also provides clinical, logistical and managerial support to the BHUs, LHWs, and dispensaries that fall within its geographical limits. RHC also provides medico-legal, basic surgical, dental and ambulance services. There are around 552 RHCs in Pakistan.

The practitioner level observations will include those of practitioners at both the private and public sector. The public sector will include observations made in outpatient departments of selected tertiary care hospitals across the study sites. Observations made at the private practitioner level will include selected solitary private clinics or clinics within private hospitals. The community and FLCF level will represent practices within the rural community and the practitioner level will represent practices within the semi urban/urban communities.

3.3 Type of Observations:

These will be participant, structured, disguised observations which will be done using a validated observation tool based on standard WHO pneumonia case management guidelines, developed in close collaboration with experts from University of Edinburgh. This tool will be pretested and translated into Urdu.

3.4 Data Collectors:

A team of data collectors, who will be healthcare professionals, will be trained on appropriate administration of the observation tool upon recruitment. The training will also include an introduction to pneumonia, its signs and symptoms, diagnosis and management according to WHO guidelines. A 3 day interactive training workshop will be conducted whereby mock excesses will also be conducted. A total of three trainings will be conducted whereby data collectors from Islamabad (capital), Punjab

and KPK will have one training as their participants can be managed to be brought in one location due to close proximity. Sindh and Baluchistan participants will have two separate trainings.

3.5 Recruitment of Disguised Patients' Caregiver and Conduction of Observations:

Each data collector will be provided a pre-defined list of addresses whereby the observations will be made. He/she will go to the location and will search the nearby community for cases of pneumonia in children under five. Once the cases have been identified, their caregivers will be sought. These caregivers are the primary individuals providing direct care to the child. Usually, these are the mothers, fathers, grandmothers or guardians of the child. They will explained the purpose of the study and will be requested to participate in the study by acting as disguised caregivers to accompany the data collector to the health facilities and upon agreement will sign a consent form. This means that they will disguise as an acquaintance of the data collector who will take them to the healthcare professional to be observed. They will take the ill child along, give the history of that child to the healthcare professional and answer any relevant questions which will be asked by him/her and get the child examined and treated. In the meantime, the data collector will make the relevant observations based on the observation tool which will be filled after the visit. The data collector will not reveal that he/she is a healthcare professional. Additionally, the data collector will also take an audio recorder along to record the entire conversation which will help in filling up the observation tool later and also validate the visit. Once the visit is completed, the data collector will take the caregiver back to their premises and fill up the observation tool in tablets within one hour of the visit.

3.6 Project work-plan:

PROJECT ACTIVITIES	YEAR 1(Months)												YEAR 2
	1	2	3	4	5	6	7	8	9	10	11	12	
Ethical Clearance	X	X											
Staff Recruitment		X											
Tool Development			X										
Inception Meetings for development of implementation strategies			X										
Pretesting and Finalization of the tool				X	X								
Data Collections (Trainings, identification of study site/centers, observations)				X	X	X	X	X	X				
Data Analysis & Reporting										X	X	X	X

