6 STUDY ASSESSMENTS

6.1 STUDY ASSESSMENTS

The following assessments will be done while doing one time observations using the observation tool (Annex A):

1. History taking: (Did the healthcare provider inquire about the presenting complaints and the predisposing factors which might have led to the complaints)
 - ✓ Cough (presenting complaint)
 - ✓ Fast breathing (presenting complaint)
 - ✓ Laboured breathing (presenting complaint)
 - ✓ Fever (presenting complaint)
 - ✓ Immunization history (Predisposing factor)
 - ✓ Breastfeeding history (Predisposing factor)
 - ✓ Overcrowding (Predisposing factor)
 - ✓ Parental smoking (Predisposing factor)

- ✓ Air pollution (Predisposing factor)
- ✓ Nutritional history (Predisposing factor)
- ✓ Hygienic practices (Predisposing factor)
- ✓ Family history of HIV (Predisposing factor)

2. Examination:

- ✓ Temperature (For fever)
- ✓ Respiratory rate for 1 minute (For fast breathing)
- ✓ Pallor (for anemia indicating malnutrition)
- ✓ Skin rash (for measles)
- ✓ Lower chest indrawing
- ✓ Auscultation for wheeze and/or crepts

3. Diagnosis:

- ✓ Cough with no fast breathing/chest indrawing: No pneumonia
- ✓ With fast breathing and/or chest indrawing : Pneumonia
- ✓ Pneumonia with any danger signs : Severe Pneumonia

4. Management:

- ✓ No Pneumonia: Symptomatic treatment
- ✓ Pneumonia: Oral amoxicillin 40mg/kg/dose twice daily for three days
- ✓ Severe Pneumonia: For LHWs: First dose of oral antibiotic (amoxicillin) and referral to health facility and for health facilities, parenteral ampicillin 50mg/kg IV 6 hourly for five days along with gentamicin 7.5mg/kg/ IM or IV for five days.

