7.1 Source Data Documentation

The checklist will be developed in the form of a structured Urdu questionnaire which will be pretested. It will then be transformed into a soft version using our online questionnaire development dashboard. The questionnaire will then be installed into tablets.

Data will be collected in tablets to avoid errors of skips and logic. It will have an essential component of not accepting incomplete forms which will ensure that complete data is being collected on site. This data will be sent to our headquarters from all over the country via online server. This will ensure rapid access to data and data confidentiality as it will only be accessed by our data manager located in the headquarters through a password restricted data dashboard.

Each data collector will be provided a tablet, its charging cable and a power-bank to ensure that the tablet is charged all the time. In case any technical error is faced in any of the tablets, he/she will inform the supervisor who will arrange an alternate tablet to enter data. Additionally, the data collector will also have extra hard copies of the questionnaires to enter data in case a technical error occurs in the tablet and if there is a delay in delivery of an alternate one. These hard copies will be sent to the project manager via courier on the same of completion of data collection to avoid delay in data entry. The data collector will also maintain a contact sheet which will include information on the location, date and time of the observation, name of the child and caregiver, phone number, observed health professional's name and level of health facility/care.

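### The plan has no rule for history the caregiver volunteers: read literally, one volunteered complaint rules out a correct history, and otherwise scoring is left to each collector

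*Combined protocol and SAP*

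**What the plan says.** **The caregiver's part.** Section 3.5 gives the caregiver two separate acts, to "give the history of that child to the healthcare professional and answer any relevant questions which will be asked by him/her". It describes no script and no instruction to hold complaints back until asked. The whole conversation is audio-recorded.

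**What an item measures.** Section 6.1 frames the history items as "Did the healthcare provider inquire about the presenting complaints and the predisposing factors which might have led to the complaints". There are 12: four presenting complaints (cough, fast breathing, laboured breathing, fever) and eight predisposing factors.

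**How the labels are formed.** Section 8.2 codes each item Y or N, with Y "meaning yes, the task was accomplished". Then: "If on history taking, the healthcare provider asks questions on all variables, then the responses will be labelled as correct"; "if any one variable is missed then the response is indicated as partially correct"; and when fewer than half of the items are asked about, the label is incorrect. Annex C sets the cut-offs at 12 for correct, above 6 and below 12 for partially correct, and below 6 for incorrect.

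**The form.** Annex C has a single Y/N column. Section 7.1 describes a tablet form "not accepting incomplete forms", so an item cannot be left blank. No section says how to score an item the caregiver mentions unprompted.

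**The concern.** The four presenting complaints are what a caregiver giving a sick child's history is most likely to say first. A provider who has just heard that the child has cough and fever has little reason to ask about them. The scoring text nevertheless credits asking, and the form forces a Y or an N.

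Correct history taking is the first of the four primary endpoints in section 2.2.1. On the literal wording it depends partly on how much the caregiver says unprompted, and the error runs towards lower labels. If collectors credit volunteered items instead, the result depends on which convention each of them adopts. Section 4.1 places two collectors in each province, ten in all. Section 3.4 trains them in three sessions: one for Islamabad, Punjab and KPK together, one for Sindh and one for Baluchistan. A convention formed by a pair of collectors or in one session would coincide with province, which is the comparison in the secondary objective and in the cross-tabulation of section 8.2.

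**Working it through.** **Plan's own figure.** Section 8.1: 6 + 4 + 4 + 9 + 9 = 32 observations per location, and 32 × 5 = 160. This reproduces; the point does not depend on it.

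**Inputs from the documents.** 4 complaints and 8 predisposing factors (6.1); correct = 12 (8.2 and Annex C); incorrect = below 6 (8.2: under 50% of 12; Annex C: below 6). A score of exactly 6 is partially correct under 8.2 and has no label in Annex C.

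**Step 1: labels without any assumed rate.** Let *k* be the number of complaints volunteered, not asked again and scored N. If the provider asks everything else, the score is 12 − *k*:

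| *k* | Score | Label |
|---|---|---|
| 0 | 12 | correct |
| 1 | 11 | partially correct |
| 2 | 10 | partially correct |
| 3 | 9 | partially correct |
| 4 | 8 | partially correct |

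With *k* = 4 the score equals the number of predisposing factors asked. It falls to 5 or less, incorrect, when at least 8 − 5 = 3 of them are not asked. If the four complaints were credited, asking 5, 4 or 3 factors would give 9, 8 or 7, partially correct.

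**Step 2: loss of the label correct.** Assume each complaint is volunteered independently with probability *v* and the provider asks everything else. The share labelled correct is (1 − *v*)^4:

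| *v* | Share correct |
|---|---|
| 0.05 | 81% |
| 0.10 | 66% |
| 0.25 | 32% |
| 0.50 | 6% |

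If volunteered items were credited, the share would be 100% in every row. The documents give no value for *v*.

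**Step 3: share labelled incorrect.** Assume each predisposing factor is asked independently with probability *p*, complaints not volunteered are always asked, and volunteered ones score N. The score is (4 − *k*) + X with X ~ Binomial(8, *p*), so P(score < 6) = P(X ≤ 1 + *k*):

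| *k* | *p* = 0.5 | *p* = 0.7 | *p* = 0.9 |
|---|---|---|---|
| 0 (or all credited) | 3.5% | 0.1% | <0.1% |
| 1 | 14% | 1% | <0.1% |
| 2 | 36% | 6% | <0.1% |
| 3 | 64% | 19% | 0.5% |
| 4 | 86% | 45% | 4% |

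**Step 4: the two cut-offs.** With *k* = 4 and *p* = 0.7, partially correct or better is P(X ≥ 6) = 55% under 8.2 and P(X ≥ 7) = 26% under Annex C. The gap is P(X = 6) = 30%, the visits that Annex C leaves without a label. If volunteered items are credited, the shares are P(X ≥ 2) = 99.9% and P(X ≥ 3) = 98.9%.

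**The case against.** - **N is not an explicit instruction.** This stands. It follows from reading 6.1 and 8.2 literally; the definition of Y as "meaning yes, the task was accomplished", and the Annex C heading, which asks whether parameters were followed, would let a collector enter Y. But then two readings are open to ten collectors, and the problem becomes inconsistent scoring. A written rule is needed either way.
- **Training, pretesting and the advisory committee could settle it.** They could, but none of those sections mentions volunteered items, and a convention of crediting them would conflict with the wording of 8.2 unless that wording is changed.
- **Asking may be the intended construct.** Section 7 describes essential care in terms of the questions a provider has to ask, so an asked-only score is defensible. That is why the fix keeps it. The same sentence ties those questions to reaching the correct diagnosis, which a volunteered cough serves as well. Crediting volunteered items also has a weakness: with four volunteered, a passive provider reaches 7, partially correct, after three questions.
- **Stronger readings.** A reader might infer that volunteered complaints turn competent histories into incorrect ones. The four complaints alone cannot: an otherwise complete history scores 8. A reader might also take 45% or 26% as the expected effect. Both assume all four complaints are volunteered at every visit and scored N, and 26% also uses the Annex C cut-off rather than that of 8.2. A bias that differs by level of care is possible, but the documents give no volunteering rates by level to support it.

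**Conclusion.** The concern holds as a gap between how the visit is run and how the history is scored. Two conclusions need no assumed rate. On the literal wording, a single volunteered complaint that is not asked again makes correct unattainable, and four limit the score to 8, partially correct. If the wording is not followed literally, scoring depends on the collector and can be confounded with province.

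The size beyond that is conditional on a volunteering rate and on *p*, neither of which is in the documents, and on independence between items. At *p* = 0.7 the share below 6 runs from about 1% with one volunteered complaint to 45% with four; at *p* = 0.9 it reaches only 4% even with four. Only the history label is affected. Examination, diagnosis and management are scored separately.

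**What to change.** 1. In Annex C and the tablet form, replace Y/N for the 12 history items with three codes: asked by provider, volunteered by caregiver, neither. Assign them with the help of the audio recording.
2. Amend 6.1 and 8.2 so that an item volunteered before the provider could ask is not counted as missed.
3. Report the history labels both ways, asked or volunteered and asked only, and name which is primary before data collection starts.
4. In the same edit, give a score of exactly 6 the same label in 8.2 and Annex C, since the size of the effect depends on it.

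The cost is one extra response code and a second tabulation; the recording and the pretest are already planned. The downside is that the asked-or-volunteered score credits information the provider did not seek, which is why the asked-only result is shown beside it.
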